Repeat dose and reproductive toxicology studies were conducted in both rats and dogs with exposure levels below those achieved at the clinical therapeutic 300 mg BID (tablet) dose (Investigator's Brochure, 2018). The repeat-dose toxicology studies of up to 6 months found that the primary target organ for toxicity was the bone marrow, with associated changes in peripheral hematology parameters, which may be related to the primary pharmacology of olaparib. All changes showed full or partial recovery following withdrawal of olaparib. Administration of olaparib during organogenesis caused reductions in early embryofetal survival and fetal weights as well as increases in the incidence of visceral and skeletal abnormalities and major eye and vertebral/rib malformations at dose levels that were not maternally toxic.

Combination of olaparib with the mono-methylating agent TMZ or topotecan suggest the potentiation of anti-tumor activity in a number of cell lines and in rats with no additional target organ toxicities compared to single agent administration (Investigator's Brochure, 2018).

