- 3.1.8 If patients have evidence of chronic hepatitis B virus (HBV) infection, HBV viral load must be undetectable on suppressive therapy if indicated. Patients with a past or resolved HBV infection (defined as the presence of hepatitis B core antibody and absence of HBsAg) are eligible.
- 3.1.9 If patients have a history of hepatitis C virus (HCV) infection, they must be treated with undetectable HCV viral load (polymerase chain reaction is negative for HCV RNA).
- 3.1.10 Patients must be postmenopausal or have evidence of non-childbearing status, OR, for women of childbearing potential, must have a negative urine or serum pregnancy test within 28 days of study treatment and confirmed again on Day 1 prior to study treatment.

Postmenopausal is defined as:

- Amenorrhoeic for \geq 1 year following cessation of exogenous hormonal treatments
- Luteinizing hormone (LH) and follicle stimulating hormone (FSH) levels in the postmenopausal range for women under 50
- radiation-induced oophorectomy with last menses >1 year ago
- chemotherapy-induced menopause with >1 year interval since last menses, or

- surgical sterilization (bilateral oophorectomy or hysterectomy)
- 3.1.11 Patients and their partners, if sexually active and of childbearing potential, must agree to the use of two highly effective forms of contraception in combination throughout the period of taking study treatment and for 3 months after the last dose of study drug(s) to prevent pregnancy in the study patient or partner.
- 3.1.12 Patients must be able to swallow orally administered medication.
- 3.1.13 Patients must have a life expectancy ≥ 16 weeks.
- 3.1.14 Patients must be able to understand and be willing to sign a written informed consent document. Patients with impaired decision-making capacity (IDMC) will be eligible if they have a close caregiver or legally authorized representative (LAR) available to assist them.
- 3.1.15 Patients must be willing and able to comply with the protocol for the duration of the study, including undergoing treatment and attending scheduled visits and examinations.

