7.2 General Principles

The following guidelines apply for dose reductions and delays:

- Dosing for a given cycle will be based on adverse events observed during the prior cycle. When multiple adverse events occur, the modification that would require the patient to receive the lowest dose combination of the study drugs is used.
- When toxicity requires a new treatment cycle to be delayed, both agents should be held until the toxicity resolves and then resumed simultaneously. Deviations from this approach should be discussed with the principal investigator.
- If toxicity requires a study agent to be held during the dosing phase (days 1-7) of a cycle, the other study agent may be continued at the investigator's discretion. If toxicity resolves, treatment with the agent that was held should generally resume at the time of the next scheduled cycle (i.e. the missed doses should not be made up). When an adverse

event results in a study agent being interrupted during a cycle, all planned assessments for that cycle will otherwise occur as scheduled.

- A subject may incur up to 2 dose reductions of each study agent prior to discontinuation of that agent. Furthermore, TMZ may not be dose reduced below 25 mg/m² daily, and olaparib may not be dose reduced below 100 mg BID; in the event reduction below such dose level is indicated, that study agent should be discontinued. However, after discontinuation of one study agent, the other study agent may be continued at the discretion of the treating investigator after an assessment of the overall risk-/benefit ratio for the patient.
- For non-hematologic adverse events that have not resolved at the scheduled start of a cycle per Section 7.1, treatment may be delayed for up to 3 weeks. If, after a 3 week delay, adverse events have still not resolved, in general the patient should be removed from the study. For the management of non-resolving hematologic toxicity, please see Section 7.4.3.

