C: A complete physical exam is performed at screening and end-of-study. A limited, symptom based, physical exam is performed at other timepoints. For patients who remain on study as of 2/2023 and live distantly (more than 50 miles) from the site, in-person clinical visits are required every other cycle. During intervening cycles, a telephone or TeleHealth visit may be conducted instead of an in-person visit. Height, weight and vital signs may be omitted. Laboratory tests, except pregnancy test, must still be performed, and can be performed in a local laboratory, prior to the start of the new cycle.

D: Vital signs includes measurement of temperature, heart rate, blood pressure, respiratory rate, and oxygen saturation (pulse oximetry).

E: CBC with diff must include: hemoglobin, red blood cells [RBC], platelets, mean cell volume [MCV], mean cell hemoglobin concentration [MCHC], mean cell hemoglobin [MCH], white blood cells [WBC], absolute differential white cell count (neutrophils, lymphocytes, monocytes, eosinophils and basophils).

Serum chemistry must include: albumin, alkaline phosphatase, total bilirubin, bicarbonate, BUN, calcium, chloride, creatinine, GGT, glucose, LDH, magnesium, phosphorus, potassium, total protein, SGOT (AST), SGPT([ALT]), sodium.

F: Coagulation factors include: aPTT, INR; required pre-study and as clinically indicated. Patients who are on anti-coagulants should have coagulation studies monitored at more frequent intervals for safety - at least once per week for the first two cycles. Local laboratory testing is acceptable.

G: Serum or urine pregnancy test (for women of childbearing potential) must be completed within 14 days of the start of study treatment, on C1D1 of the study prior to commencing treatment, at each subsequent visit during study treatment, and at the follow up visit. Tests will be performed by the treating institution/hospital's laboratory. If results are positive the patient is ineligible and must be discontinued from study treatment immediately. Details of the pregnancy tests must be recorded in the patient's medical records.

H A 12-lead ECG is performed at screening and end-of-study. Additional ECGs are performed as clinically indicated.

I: MRI or CT imaging to evaluate disease status is performed at baseline and once every 2 cycles (6 weeks) \pm 3 days. For patients who continue beyond 12 cycles, MRI or CT imaging may be changed to once every 4 cycles (12 weeks) \pm 3 days

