J: See section 5.4.5 for details on sample collection.

- K: Start- of cycle safety assessments may be performed up to 3 days prior to initiating treatment for a new cycle. Local laboratory testing is acceptable.
- L: Between cycle safety assessments may be performed ± 3 days from scheduled date. Local laboratory testing is acceptable. If there is a change in the patient's clinical condition after the laboratory testing is complete but before dosing begins, testing should be repeated.
- M:: Pre-study biopsy is performed within 14 days of C1D1. On study biopsy is performed on day 3-5 of Cycle 2. If the start of C2 is delayed, the biopsy should be delayed accordingly to match actual drug administration of C2 D3-5. See Correlative Studies section 5 for additional information.
- N: Selected patients undergo an optional third tumor biopsy in the event of radiographic progression after initial evidence of clinical benefit. See Section 5.4.2 for details.

TMZ=temozolomide; PO=oral administration, BID=twice per day, QD=once per day; BUN=blood urea nitrogen; GGT=gamma galactosyltransferase; LDH=lactic dehydrogenase; SGOT(AST)=serum glutamic oxaloacetic transaminase (aspartate transaminase); SGPT(ALT)=serum glutamic pyruvic transaminase (alanine transaminase); aPTT=activated partial thromboplastin time; INR=international normalized ratio; MRI=magnetic resonance imaging; CT=computerized tomography; ECG=electrocardiogram; POD=progression of disease.

All time windows refer to business days (e.g. exclude weekends and holidays).

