Pregnancy tests on blood or urine samples will be performed for women of childbearing potential within 14 days prior to the start of study treatment, on Day 1 of the study prior to commencing treatment, at each subsequent visit during study treatment, and at the follow up visit. Tests will be performed by the hospital's local laboratory. If results are positive the patient is ineligible/must be discontinued from study treatment immediately. Details of the pregnancy tests must be recorded in the patient's medical records.

These tests will be performed by the hospital's local laboratory. Additional analyses may be performed if clinically indicated. Local laboratory testing is acceptable as indicated in the study calendar, except for pregnancy testing, which should be performed by the treating institution/hospital's local laboratory.

Any clinically significant abnormal laboratory values should be repeated as clinically indicated and recorded on the eCRF.

In case a patient shows an AST or ALT $\geq 3 \times ULN$ or total bilirubin $\geq 2 \times ULN$, please refer to Appendix F, "Actions Required in Cases of Combined Increase of Aminotransferase and Total Bilirubin – Hy's Law", for further instructions. In addition, evaluate patients for potential drug-induced liver injury (DILI) as described in Section 10.3.4.

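### In optional telehealth cycles the Study Calendar waives only the pregnancy test, and no laboratory outside the treating institution may do it, so a woman of childbearing potential would be tested every 42 days instead of every 21.

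*Combined protocol and SAP*

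**What the plan says.** All references are to the combined protocol and SAP.

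- **Default schedule.** The Section 11 calendar marks a pregnancy test in weeks 1, 4 and 7, the first week of each cycle. Footnote G specifies "Serum or urine pregnancy test (for women of childbearing potential") and asks for it at screening, on day 1 of cycle 1 before dosing, at every later on-treatment visit and at follow-up. A positive result means immediate discontinuation of study treatment.
- **Where it is done.** Footnote G: "Tests will be performed by the treating institution" or hospital laboratory. Section 11.1 agrees: "Local laboratory testing is acceptable as indicated in the study calendar, except for pregnancy testing".
- **Telehealth option.** Footnote C applies to distant patients still on study in 2/2023. It requires an in-person visit every other cycle and permits a remote visit in between. For the remote cycles: "Laboratory tests, except pregnancy test, must still be performed, and can be performed in a local laboratory", before the cycle starts.
- **Other pre-cycle tests.** Under footnote K, start-of-cycle "safety assessments may be performed up to 3 days prior to initiating treatment for a new cycle", and local testing is acceptable.

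**The concern.** Among the pre-cycle laboratory tests, the pregnancy test is the only one footnote C releases. The protocol gives no reason for this, although it treats fetal exposure as a serious hazard. Section 2.2.1.2 reports: "Administration of olaparib during organogenesis caused reductions in early embryofetal survival and fetal weights", together with malformations, at doses that were not toxic to the mother. Section 3.2.13 excludes pregnant women because of teratogenic or abortifacient potential.

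At stake is how soon the schedule would detect a pregnancy in a woman using the telehealth option. She would take a 7-day course of olaparib and temozolomide in every second cycle with no protocol-required test at its start. The need to travel does not explain the gap: she must have blood drawn before that cycle anyway, and may have it drawn locally.

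**Working it through.** The plan states no figure to reproduce. The check sets the provisions side by side and then works out the testing interval.

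**1. Is the test required before a telehealth cycle?** There are two readings of footnote C.
- *Natural reading:* the exception removes the pregnancy test from the tests that must be done. No test is then due.
- *Narrower reading:* the exception limits only the permission to use a local laboratory. The test is then still due under footnote G, because a remote visit is a visit, but it must be done at the treating institution, where the patient is not.

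On the first reading the test is waived. On the second it is due but cannot be done remotely. The text needs repair either way.

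**2. Could it be done elsewhere under the current text?** Footnote G and Section 11.1 both tie it to the treating institution's laboratory, and no section provides an alternative. Footnote G accepts serum or urine, so the restriction is on place and not on type of test.

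**3. Interval between required tests.** Inputs: cycle length 21 days (Section 6.1); dosing on days 1–7 (Section 6.1); in-person visit every second cycle (footnote C). I assume that tests fall at the start of each in-person cycle, that cycles run on schedule, and that the ±2-day cycle window is ignored.

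| | Visit every cycle | Telehealth option |
|---|---|---|
| Days between required tests | 1 × 21 = 21 | 2 × 21 = 42 |
| Age of last negative test at start of an in-person course | about 0 days | about 0 days |
| Age of last negative test at start of a telehealth course | not applicable | about 21 days |
| Courses with no required test at their start | 0 in 2 | 1 in 2 |

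**4. How many women?** The documents do not say. The upper bound is the 22 participants (Section 5.7.1.3). An affected woman must also have been on study in 2/2023, live more than 50 miles away, use the optional remote visit and be of childbearing potential. Section 3.1.10 counts "surgical sterilization (bilateral oophorectomy or hysterectomy") as non-childbearing status, which in uterine leiomyosarcoma is likely to remove most patients. Eligibility does not require hysterectomy, however, and Section 3.1.2 admits locally advanced unresectable disease, so zero is plausible but not established.

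**The case against.** The best case for leaving the text alone is that the exemption is explicit and matches the rule that pregnancy tests belong at the treating institution. Its 2/2023 cut-off coincides with Amendment 8 of February 14, 2023, so it was written for a small group already under care. The option is voluntary, so a site can bring a woman of childbearing potential in every cycle under the present wording. Tests may be added when clinically indicated (Section 11.1). Two-method contraception (Section 3.1.11), prompt self-report of suspected pregnancy (Section 6.3) and in-person testing in alternate cycles all continue.

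Most of this stands, and it keeps the point minor. It does not explain why this one test is left out when blood must be drawn before the same cycle. The remaining safeguards are also not equivalent to a scheduled test. Self-report depends on the patient suspecting pregnancy. Section 6.2.3.4 warns that hormonal contraceptives may be less effective with olaparib, while Appendix G accepts hormonal methods with a male condom.

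A reader might infer three stronger claims that the documents do not support.

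- *That the stopping rule fails without a pre-dose test.* Footnote G acts on any positive test, and Section 6.3 makes pregnancy a separate reason to end treatment, including after self-report. The waiver delays scheduled detection; it does not disable the rule.
- *That the gap reaches 63 days.* Section 7.2 says "treatment may be delayed for up to 3 weeks", and 42 + 21 = 63. But that allowance is for unresolved non-hematologic adverse events, and the figure assumes no in-person visit during a toxicity hold, which nothing in the protocol supports. Delays also lengthen the interval under per-cycle testing: an interruption of 4 weeks, the limit in Section 7.9 before the case goes to the medical monitor, gives 21 + 28 = 49 days. Only the missing test at the start of the telehealth cycle is due to footnote C.
- *That a home test is the obvious remedy.* It would replace a laboratory result with a self-reported one. That trade-off is debatable, and it is unnecessary when a laboratory draw is already required.

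**Conclusion.** The point holds as a minor safety matter. For patients who use the telehealth option, footnote C waives the pregnancy test in alternate cycles and keeps every other pre-cycle laboratory test, while footnote G and Section 11.1 rule out testing outside the treating institution. For a woman of childbearing potential on schedule, the interval between required tests doubles from 21 to 42 days, and every second course starts on a negative result about 21 days old.

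This rests on the natural reading of footnote C and on the timing assumptions above. Under the narrower reading the consequence changes, from no test to a test that cannot be done remotely, but the need for repair does not. The number of women affected is unknown and may be zero. The primary endpoint, sample size and error rates are unaffected.

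**What to change.** Three wording changes in the next amendment:

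1. **Footnote C:** delete the words that except the pregnancy test. Add that women of childbearing potential have a serum or urine pregnancy test at the local laboratory with the required pre-cycle blood draw, and that a negative result is recorded before the first dose of the telehealth cycle.
2. **Footnote G:** after the sentence on where tests are done, add *except before telehealth cycles (footnote C), when a local-laboratory test is acceptable*.
3. **Section 11.1:** add the same exception. This section uses *local* for the treating hospital's own laboratory, so it should state that a laboratory near the patient is meant.

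The cost is one inexpensive test per telehealth cycle, with no extra visit, plus the wording changes and their review. If no remaining patient is of childbearing potential, nothing changes in practice.

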11.1 Laboratory Assessments

Full hematology assessments for safety (hemoglobin, red blood cells [RBC], platelets, mean cell volume [MCV], mean cell hemoglobin concentration [MCHC], mean cell hemoglobin [MCH], white blood cells [WBC], absolute differential white cell count (neutrophils, lymphocytes, monocytes, eosinophils and basophils) and absolute neutrophil count or segmented neutrophil count and band forms should be performed at each visit and when clinically indicated. If absolute differentials are not available, please provide % differentials.

Serum biochemistry assessments for safety include sodium, potassium, calcium, magnesium, fasting glucose, creatinine, total bilirubin, gamma galactosyltransferase (GGT), alkaline phosphatase (ALP), aspartate transaminase (AST), alanine transaminase (ALT), urea or blood urea nitrogen (BUN), total protein, albumin, and lactic dehydrogenase (LDH). These assessments should be performed at every clinic visit and when clinically indicated.

Coagulation (activated partial thromboplastin time [aPTT] and INR) will be performed at baseline and if clinically indicated unless the patient is receiving warfarin. Patients taking warfarin may participate in this study; however, it is recommended that prothrombin time (INR and aPTT) be monitored carefully at least once per week for the first two cycles.

Bone marrow or blood cytogenetic samples may be collected for patients with prolonged hematological toxicities as defined in Section 7.4.3. Bone marrow analysis should include an aspirate for cellular morphology, cytogenetic analysis and flow cytometry, and a core biopsy for bone marrow cellularity. If it is not possible to conduct cytogenetic analysis or flow cytometry on the bone marrow aspirate, then attempts should be made to carry out the tests on a blood sample. Full reports must be provided by the investigator for documentation on the Patient Safety database. These data are not required to be entered into CRF.

Pregnancy tests on blood or urine samples will be performed for women of childbearing potential within 14 days prior to the start of study treatment, on Day 1 of the study prior to commencing treatment, at each subsequent visit during study treatment, and at the follow up visit. Tests will be performed by the hospital's local laboratory. If results are positive the patient is ineligible/must be discontinued from study treatment immediately. Details of the pregnancy tests must be recorded in the patient's medical records.

These tests will be performed by the hospital's local laboratory. Additional analyses may be performed if clinically indicated. Local laboratory testing is acceptable as indicated in the study calendar, except for pregnancy testing, which should be performed by the treating institution/hospital's local laboratory.

Any clinically significant abnormal laboratory values should be repeated as clinically indicated and recorded on the eCRF.

In case a patient shows an AST or ALT $\geq 3 \times ULN$ or total bilirubin $\geq 2 \times ULN$, please refer to Appendix F, "Actions Required in Cases of Combined Increase of Aminotransferase and Total Bilirubin – Hy's Law", for further instructions. In addition, evaluate patients for potential drug-induced liver injury (DILI) as described in Section 10.3.4.

11.2 ECG

ECGs are required within 14 days prior to starting study treatment, at the end of study treatment, and when clinically indicated.

Twelve-lead ECGs will be obtained after the patient has been rested in a supine position for at least 5 minutes in each case. The investigator or designated physician will review the paper copies of each of the timed 12-lead ECGs on each of the study days when they are collected. ECGs will be recorded at 25 mm/sec. All ECGs should be assessed by the investigator as to whether they are clinically significantly abnormal / not clinically significantly abnormal. If there is a clinically significant abnormal finding, the Investigator will record it as an AE on the eCRF. The original ECG traces must be stored in the patient medical record as source data.

12. MEASUREMENT OF EFFECT

12.1 Antitumor Effect – Solid Tumors

For the purposes of this study, patients should be re-evaluated for response every 6 weeks. In addition to a baseline scan, confirmatory scans should also be obtained 6 weeks (not less than 4) weeks following initial documentation of objective response. For patients who continue beyond 12 cycles, MRI or CT imaging may be changed to once every 4 cycles (12 weeks) \pm 3 days

Response and progression will be evaluated in this study using the new international criteria proposed by the revised Response Evaluation Criteria in Solid Tumors (RECIST) guideline (version 1.1) (Eisenhauer *et al.*, 2009). Changes in the largest diameter (unidimensional measurement) of the tumor lesions and the shortest diameter in the case of malignant lymph nodes are used in the RECIST criteria.

